## 10) Research Setting

Data will be collected at the UNM hospital pediatric surgical suites.

## 11) Study Methods

This is a prospective observational study. Prospectively-recorded data are necessary because data on the outcomes of interest are not available in the medical record.

Participants will be enrolled in the study once they have entered the pre-operative area and they are determined by the attending anesthesiologist to

that they are an eligible study participant. Participants enrolled in the first three months of the study will be assigned to the baseline condition as described below. Participants enrolled in the second phase of the study will be assigned to the with-cannula condition described below.

A patient sticker will be added to the data collection form. Basic demographic information and vitals will be recorded before premedication is administered as is standard at entry to the pre-operative area. Timing devices of the same make and model will be used consistently between all study cases.

For the **baseline group** of this observational study, all intubation procedures will be performed as per usual practice. Patients will receive premedication as determined by anesthesiologist/resident/midlevel, and the type and dose will be recorded.

Once patients are brought to the operating room suite and vital signs are being monitored, patients will be preoxygenated via mask per standard of care, with an expired oxygenation concentration minimum of 0.75. Vitals will be recorded at the moment prior to removal of the face mask at the end of the preoxygenation period. Anesthetic induction will then be performed with agents and dosages as per the provider's clinical judgment.

Airway management consisting of oral endotracheal intubation or laryngeal mask airway insertion will take place. As per usual practice, an attending physician who is expert in pediatric airway management will supervise the procedure and intervene before the patient experiences excessive oxygen desaturation. The lowest oxygen saturation and the time to either successful intubation or intervention by an attending physician will be recorded.

For the **with-cannula group**, all of the above steps will be maintained. The sole difference will be nasal cannula placement after induction. It will be set to deliver 5L of oxygen per minute.

Airway management consisting of oral endotracheal intubation or laryngeal mask airway insertion will take place. As per usual practice, an attending physician who is expert in pediatric airway management will supervise the procedure and intervene before the patient experiences excessive oxygen desaturation. The lowest oxygen saturation and the time to either successful intubation or intervention by an attending physician will be recorded. Apneic oxygenation will not be used as a long-term oxygenation strategy. No patient will be allowed to cross any particular SPO2 threshold solely for research reasons.

All intubation procedures in both study groups will proceed as per usual practice. The goal of all intubation procedures has always been and remains the maintenance of adequate oxygen saturation.

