Taha et al 2006, concluded the use of nasal cannula insufflation after preoxygenation can delay the onset of hemoglobin desaturation for a prolonged period of time during the subsequent apneic period in adults. Ramachandran et al 2009, demonstrated the ability to prolong oxygen saturations >95% and increase the lowest saturation level with use of a nasal cannula at 5 L/min during simulated difficult intubations in adult obese males. Weingart and Levitan 2012, recommend that nasal cannula apneic oxygenation can extend the safe apnea period after the use of sedatives and muscle relaxants in adults. With a variety of search terms only three relevant articles were found in pediatric anesthesia literature. Bhagwan 2013, in Pediatric Anesthesia, commented about Levitan's NoDesat article in EPmonthly 2012, endorsing how her use of the nasal cannula adjunct in the peri-intubation period has led to fewer desaturations and bradycardic episodes in infant intubations by resident physicians. Her opinions were based on her experiences, but no data was gathered or presented to support the claims in a form representing a true study. T.M. Cook 1998, wrote a paper discussing blood gas results during pediatric apneic oxygenation in intubated pediatric patients undergoing undergoing cardiac catheterization. The findings demonstrated that apneic oxygenation was likely safe for up to 10 minutes before hypoxia would occur. An earlier study by Kernisan et al 1987, also studied apneic oxygenation in pediatric patients. Patients were intubated and not ventilated and they found desaturation via pulse oximetry did not occur in patients at 3 minutes.

Physiologically, children have a higher oxygen consumption than adults, 5-10 mL/kg/min, compared to adults, 3mL/kg/min. This high metabolic rate leaves pediatric patients at higher risk for hemoglobin desaturation in the peri-intubation period. In a Hospital setting there can be prolonged time periods as airway devices are placed in certain patients. The current

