**12) List of Appendices**

Data collection form

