**14) Data Management**

Only study investigators will have access to study data. Study participants will be assigned a study number, and this number will be used in all data analyses. The data will be entered into an electronic database that will be stored on UNMHSC password-protected servers. The electronic data will only have study participant numbers and no identifiers that could link specific patients to the data. All data forms that bear identifiers will be securely destroyed (shredded) upon application to HRRC for study closure, so that only deidentified data remain when that application is made.

As noted above, data to be gathered include basic demographic data, data about the anesthetic induction procedure, and data about the patient's O2 saturation.

Routine demographic data will be analyzed with t-tests and Wilcoxon rank-sum tests, as appropriate depending on normality of data distributions. Categorical data will be analyzed with appropriate analyses, such as chi-square, Fisher's exact, risk ratio, and/or odds ratio.

The primary outcome of time to cross the 95% saturation threshold will be analyzed with Kaplan-Meier curves and survival analysis with "censoring" for cases in which the threshold was not crossed because of either successful intubation or intervention by the attending physician.

Secondary outcomes with continuous data (e.g. the lowest observed O2 saturation) will be analyzed with standard t-tests or Wilcoxon rank-sum tests, as appropriate depending on normality of data distributions. Secondary outcomes with binary data (e.g. whether intervention by the attending physician is required) will be analyzed with chi-square or Fisher's Exact tests as appropriate depending on cell counts.

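### Preoxygenation has a floor but no planned between-phase comparison or adjustment, so any difference in expired oxygen between the two calendar periods would be confounded with the cannula effect

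*Combined protocol and SAP*

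**What the plan says.** All references are to the combined protocol and SAP.

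- **Allocation (section 11).** "Participants enrolled in the first three months of the study will be assigned to the baseline condition as described below". Children who come later, in a second phase, form the with-cannula group. The comparison is sequential and not randomised.
- **Preoxygenation (section 11).** Both groups are preoxygenated by mask under usual care, "with an expired oxygenation concentration minimum of 0.75". No target or upper value is given.
- **What is recorded at that moment (section 11).** "Vitals will be recorded at the moment prior to removal of the face mask at the end of the preoxygenation period". Expired oxygen is not named.
- **Comparability (section 11).** The with-cannula group keeps every other step. "The sole difference will be nasal cannula placement after induction".
- **Data items (sections 12 and 14).** Section 14 lists demographics, "data about the anesthetic induction procedure, and data about the patient's O 2 saturation". Section 12 lists one appendix, "Data collection form", whose content is not in the supplied text.
- **Primary analysis (sections 3 and 14).** The outcome is time from induction to an SpO2 of 95%. It is analysed with Kaplan-Meier curves and survival analysis. No covariate is named, and no comparison of preoxygenation between phases is described.

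**The concern.** The cannula is meant to delay desaturation by getting more oxygen to the lungs. The oxygen already in the lungs when the mask comes off should act on the same quantity. This is physiological reasoning, not something the protocol states, but it follows the mechanism in section 4, which also notes that "children have a higher oxygen consumption than adults, 5-10 mL/kg/min".

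A floor fixes the lower end of expired oxygen and leaves the rest to the provider. Providers can see which phase they are in. In a randomised trial, variation above the floor would be balanced on average. Here nothing balances it, and the statement that the cannula is the only difference is an assumption that the named data cannot check. SpO2 at mask removal is a weak substitute, because it can sit at its ceiling over a range of expired oxygen values.

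At stake is the interpretation of the primary result. Fuller preoxygenation in the second phase would look like a cannula benefit. Less full preoxygenation, for instance because providers rely on the cannula, would hide one.

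**Working it through.** **1. The plan's own figure.** Section 6 gives 371 patients for 80% power, one-tailed logrank test, alpha 0.05, and a 15% event rate that is halved. Freedman's formula with a hazard ratio (HR) of 0.5 gives

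(1.645 + 0.842)² × [(1 + 0.5)/(1 − 0.5)]² = 55.64 events, and 55.64/0.15 = 370.95, that is 371.

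This reproduces the figure, with the 15% rate applied to both arms. It confirms the type of test to use below. The 94% power that section 6 quotes for 400 patients is a separate matter and is not used here.

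**2. Effect of a drift with no cannula effect.** Inputs from section 6: 200 per group, 15% baseline rate, one-sided 5% test. Assumption: preoxygenation alone changes the second-phase rate to x. Then

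- HR = ln(1 − x)/ln(1 − 0.15)
- events d = 400 × (0.15 + x)/2
- z = √d × (1 − HR)/(1 + HR) − 1.645, and the chance of significance is Φ(z).

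| x | HR | d | z | Chance of one-sided significance |
|---|---|---|---|---|
| 15% (no drift) | 1.000 | 60 | −1.645 | 5% |
| 13% | 0.857 | 56 | −1.068 | 14% |
| 12% | 0.787 | 54 | −0.767 | 22% |
| 10% | 0.648 | 50 | −0.136 | 45% |

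**3. Drift the other way.** If the cannula truly halves the rate to 7.5%, then HR = 0.480, d = 45, z = 0.714, and power is 76%. If poorer preoxygenation makes that 7.5% appear as 10%, the chance of significance falls to 45%, as in the last row of the table.

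**4. Whether adjustment would help.** The documents give no distribution of expired oxygen, so this step is a simulation on assumed inputs: 200 per group, no cannula effect, baseline mean 0.82 and SD 0.04 with values held at or above 0.75, log-normal time to 95% proportional to expired oxygen, a 15% baseline event rate, and 800 runs per setting. The ranges cover a log-SD of 0.3 to 0.5.

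| Rise in second-phase mean | Unadjusted Cox, false positives | Adjusted for expired oxygen |
|---|---|---|
| 0 | 4–5% | about 5% |
| 0.02 | 8–14% | 5% |
| 0.05 | 19–33% | 5–6% |

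Adjustment works this well partly because the simulated covariate is complete and measured without error.

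**The case against.** Several points on the other side stand.

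- **A reader might infer that expired oxygen is not recorded.** The documents do not show that. Vitals are taken at the moment the value would be read, section 14 includes induction data in general terms, and the data collection form may hold the field. The supportable statement is that the variable is not named. Even if it is on the form, section 14 has no plan to use it.
- **A reader might infer that preoxygenation will improve in the second phase, for example through training.** Section 6 speaks of education on the nasal cannula, not on mask preoxygenation. Section 11 holds the floor and the other steps constant. No drift is documented, and neither direction is favoured.
- **A reader might take a store-duration calculation as the size of the bias.** With an assumed lung volume of 20–30 mL/kg and the protocol's consumption of 5–10 mL/kg/min, the store lasts 20 × 0.75/10 × 60 = 90 s to 30 × 0.75/5 × 60 = 270 s at 0.75, and 108 to 324 s at 0.90. The gap of 18 to 54 s compares two hypothetical children. Bias depends on the difference between phase means, which is unknown. In the same figures, lung volume and consumption move the duration threefold, against 20% for expired oxygen.
- **The simulated shift of 0.05 is large.** It is 1.25 of the assumed SDs (0.05/0.04). It shows what could happen, not what is likely.
- **This is one case of a wider weakness**, an unadjusted before-after comparison. Premedication, induction agents and doses are also left to the provider. That is true, but expired oxygen is a specific co-treatment that adjustment for demographics would not capture.
- **Adjustment can introduce its own problem.** Missing values may cluster in children who tolerate the mask poorly. With about 200 × 0.15 + 200 × 0.075 = 45 events expected at the planned rates, losing some of them selectively would matter. The fix therefore needs a missing-data rule.

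**Conclusion.** The point holds in a conditional form. The groups are sequential, preoxygenation has only a floor, and no planned analysis compares expired oxygen between phases or adjusts for it. A between-phase difference above the floor would therefore be confounded with the cannula effect, and could create an apparent benefit or mask a real one.

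The size of any actual bias cannot be given. The figures of 14%, 22% and 45% rest on the planned 200 per group, the 15% baseline rate, proportional hazards, and a drift assumed to produce the stated event rates. They show that a fall of two to five percentage points in the event rate, with no cannula effect, is enough to distort a one-sided 5% test materially. They do not show that such a fall is expected.

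This is an inexpensive improvement worth making. It is not evidence that the comparison is already biased.

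**What to change.** - **Section 11:** state that the expired oxygen concentration is recorded with the vitals at mask removal, in both phases. If the data collection form already has the field, say so.
- **Section 14, description:** report its distribution by phase, with the number of missing values and of values below 0.75 in each phase.
- **Section 14, analysis:** alongside the Kaplan-Meier analysis, prespecify a Cox model for time to 95% with phase and expired oxygen as a continuous covariate. The value is taken before the cannula is placed, so adjusting for it does not remove any effect of the cannula itself.
- **Missing values:** state the rule in advance, for example multiple imputation with phase and outcome in the imputation model, so that children who tolerate the mask poorly are not dropped.
- **Sensitivity analysis:** repeat the analysis in children with a recorded value of at least 0.75. It should not replace the analysis of all enrolled children.

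The cost is one number that the provider must already read to know the floor was met, one covariate, and one sensitivity analysis. Some values will be missing. The value must be captured before study closure, when sections 13, 14 and 25 have the identifiable forms and the identity link destroyed. No change to clinical care is proposed.

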**12) List of Appendices**

Data collection form

**13) Data and Specimen Banking**

Deidentified data will be retained indefinitely in electronic format after study completion. This retention will be only for possible use in preparation for future studies involving one or more of the investigators on this study, such as to inform power analyses. While future studies are not currently planned, they may include investigations of the optimal use of and indications for pediatric apneic oxygenation, for example. All retained data will be stripped of all 18 HIPAA identifiers and stored on UNMHSC password-protected servers. The paper data collection forms and link to identity will not be retained, but will be shredded upon study completion.

**14) Data Management**

Only study investigators will have access to study data. Study participants will be assigned a study number, and this number will be used in all data analyses. The data will be entered into an electronic database that will be stored on UNMHSC password-protected servers. The electronic data will only have study participant numbers and no identifiers that could link specific patients to the data. All data forms that bear identifiers will be securely destroyed (shredded) upon application to HRRC for study closure, so that only deidentified data remain when that application is made.

As noted above, data to be gathered include basic demographic data, data about the anesthetic induction procedure, and data about the patient's O2 saturation.

Routine demographic data will be analyzed with t-tests and Wilcoxon rank-sum tests, as appropriate depending on normality of data distributions. Categorical data will be analyzed with appropriate analyses, such as chi-square, Fisher's exact, risk ratio, and/or odds ratio.

The primary outcome of time to cross the 95% saturation threshold will be analyzed with Kaplan-Meier curves and survival analysis with "censoring" for cases in which the threshold was not crossed because of either successful intubation or intervention by the attending physician.

Secondary outcomes with continuous data (e.g. the lowest observed O2 saturation) will be analyzed with standard t-tests or Wilcoxon rank-sum tests, as appropriate depending on normality of data distributions. Secondary outcomes with binary data (e.g. whether intervention by the attending physician is required) will be analyzed with chi-square or Fisher's Exact tests as appropriate depending on cell counts.

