## 6) Number of Subjects (Recruitment Target)

A sample size estimate based on prior studies of apneic oxygenation in adults indicates that approximately 400 subjects would be appropriate for this study, 200 in the baseline group without nasal cannula adjunct and 200 patients with implementation of nasal cannula adjunct during the peri-intubation period.

A power analysis (based on formulae in *Statistics in Medicine* 1982; 1:121-9) indicated that if the baseline rate of reaching 95% SPO2 is 15% of patients and this procedure reduces that rate by half, 80% power at  $\alpha=0.05$  is reached for a one-tailed logrank test with a total of 371 patients. Rounding up to 400 patients to accommodate incomplete datasheets would provide power of 94%.

Based on enrollment rate to date, we estimate that enrollment of 400 patients will take approximately one year. Because the planned evaluation of routine use of nasal cannula adjunct oxygenation is occurring independent of enrollment counts to the baseline study condition, data

may be gathered on more than 200 patients in that group. In order to permit analysis without loss of power, we may need to enroll a higher total sample size in order to achieve an equal sample size in the group with the cannula. To accommodate this reality, we may enroll a maximum of 500 patients in the entire study.

This period will also permit education of all relevant providers and staff on the use of peri-intubation nasal cannula oxygenation.

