## 9) Study Endpoints

As this study is of minimal intervention and minimal risk, we do not anticipate early study termination for research-induced adverse outcomes. The planned intervention may be suspended or canceled after the interim analysis if it is ineffective, or if we reach statistical significance on the primary outcome halfway through collecting our estimated number of patients. “Ineffectiveness” is defined here as a failure to identify one-tailed superiority of the with-cannula group with  $p < 0.20$  on *any* of the outcomes (primary or secondary) at the interim analysis.

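### The two groups are consecutive calendar periods, yet no covariate adjustment is specified, so a recorded case-mix difference would be counted as a cannula effect or could hide one

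*Combined protocol and SAP*

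**What the plan says.** **Allocation.** Section 11: "Participants enrolled in the first three months of the study will be assigned to the baseline condition as described below". Later enrolees form the with-cannula group.

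**Primary outcome.** Section 14: "The primary outcome of time to cross the 95% saturation threshold will be analyzed with Kaplan-Meier curves and survival analysis". Nothing further is said about the form of the survival analysis beyond the handling of censoring. Section 6 states that 80% power "is reached for a one-tailed logrank test with a total of 371 patients"; this is the only survival test named.

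**Secondary outcomes.** Section 14: "Secondary outcomes with binary data (e.g. whether intervention by the attending physician is required) will be analyzed with chi-square or Fisher's Exact tests". Continuous secondary outcomes have t or rank-sum tests.

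**Baseline data.** Section 14: "Routine demographic data will be analyzed with t-tests and Wilcoxon rank-sum tests, as appropriate depending on normality of data distributions". The plan does not say what follows if these tests show a difference.

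**Interim.** Section 9 allows the intervention to be suspended or cancelled for ineffectiveness on any outcome, or "if we reach statistical significance on the primary outcome halfway through collecting our estimated number of patients".

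**Safeguards.** There is one site (Sections 10 and 20), every eligible patient is enrolled (Section 7), and ASA classes 4-6 are excluded (Section 5). For the cannula group "all of the above steps will be maintained", including the preoxygenation minimum and expert supervision (Section 11). Near-complete data capture is sought (Section 29).

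**The concern.** Randomisation would balance risk factors between groups on average. Consecutive periods do not. Eligible children range from 40 weeks adjusted gestational age to 8 years (Section 5) and receive either a tube or a laryngeal mask (Sections 8 and 11). Learners routinely intubate (Section 4), and induction agents are left to the provider (Section 11). Enrolling 400 patients is expected to take about a year (Section 6). The safeguards limit selection and procedural drift, but none makes the age or device mix the same in the two periods.

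If the cannula period happens to have lower-risk patients, the unadjusted comparison rejects too often when the cannula does nothing. If it has higher-risk patients, a real benefit is diluted and power falls. Either could also affect the interim decision in Section 9. Without a prespecified adjustment, any covariates added later would be chosen after the data had been seen.

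**Working it through.** **1. Is any adjustment specified?** Sections 6, 9, 11 and 14 are the only places that describe analysis or allocation. None names a covariate, stratified test, regression model, matching, weighting or calendar-time term.

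**2. The plan's own figure.** Inputs from Section 6: 15% halved to 7.5%, one-tailed 0.05, 80% power, 371 patients. The Freedman events formula with hazard ratio 0.5 gives (1.645 + 0.842)² × (1.5/0.5)² = 6.183 × 9 = 55.64 events, and 55.64 / 0.15 = 370.95. So 371 is reproduced only by applying the 15% rate to both groups. That discrepancy is a separate matter and nothing below depends on it. What matters here is that the calculation is for an unadjusted logrank.

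**3. Events available on the plan's own rates.**
- Final: 200 × 0.15 + 200 × 0.075 = 45.
- Interim, halfway through the cannula group (Section 8): 200 × 0.15 + 100 × 0.075 = 37.5.
- If the baseline rate were 10% (assumed; Section 18 describes rates as very low): 200 × 0.10 + 200 × 0.05 = 30.

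A Cox model with three terms (group, age, SpO2) and device as a stratum therefore has 45/3 = 15 events per term at the end, 37.5/3 = 12.5 at the interim, and 10 in the low-rate case.

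**4. Age shift, no cannula effect.** Assumed: the hazard falls fourfold from birth to 8 years, so the log hazard changes by ln(0.25)/8 = −0.173 per year; baseline risk is 15%, with 200 per group. Let e be the expected events in the cannula group. The rejection probability is Φ(shift/SE − 1.645), with SE = √(1/30 + 1/e).

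| Cannula group older by | Spurious hazard ratio | e | SE | False positives |
|---|---|---|---|---|
| 0.5 year | 0.917 | 27.5 | 0.264 | Φ(0.328 − 1.645) = 9% |
| 1 year | 0.841 | 25.2 | 0.270 | Φ(0.641 − 1.645) = 16% |

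Simulation (exponential event times; assumed lognormal censoring with median 45 s and log-SD 0.5) gives about 10% and 15-17% for the logrank, depending on how the age distribution is shifted. A Cox model with group, age and an uninformative SpO2 term gives about 5%.

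**5. Age shift, risk truly halved.** The same simulation set-up, with the cannula group younger by 0, 0.5 or 1 year, gives power of about 79%, 70% and 62% for the logrank. The adjusted model stays at 78-79%.

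**6. Device shift, no cannula effect.** Two-proportion test, pooled null variance, 200 per group, 50% laryngeal masks at baseline. All risks and shifts are assumed.

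| Risk, tube / mask | Mask share in cannula period | Overall risk | False positives |
|---|---|---|---|
| 18% / 12% | 55, 60, 65% | 14.7, 14.4, 14.1% | 6, 7, 8% |
| 22% / 8% | 55, 60, 65% | 14.3, 13.6, 12.9% | 7, 11, 15% |

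In simulation of the 22% / 8% case, a device-stratified logrank stays at 5%.

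**7. Scale of the shifts.** The chance standard error of a difference in device share is √(2 × 0.25/200) = 5 points. For mean age, with ages uniform over 0-8 years, it is √(2 × (64/12)/200) = 0.23 years. A shift of 0.5 or 1 year is thus about 2 or 4 standard errors.

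**The case against.** **The primary analysis is unspecified, not unadjusted.** A reader might infer that the plan commits to an unadjusted primary test. It does not: survival analysis is a generic term that leaves room for a Cox model, and the logrank appears only in the power paragraph. Only the secondary tests are unadjusted as written. This stands and limits the point to an omission. An open term still offers no protection, since nothing is fixed in advance.

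**No drift is shown.** A reader might infer that the result will be biased. Nothing in the documents shows that age or device mix changes between periods, and site, eligibility and procedures stay constant. Chance imbalance alone does not inflate the overall error rate: with both periods drawn from one device mix, simulation gives 5.1%. The larger figures need a systematic shift. This stands, so the figures are illustrations only.

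**Adjustment does not rescue a before-after design.** A reader might infer that it does. Unmeasured drift, such as growing learner experience or the staff education mentioned in Section 6, remains. If underlying risk fell from 15% to 13% or 12% for unrecorded reasons, a device-stratified test would still reject about 14% or 23% of the time. This stands and must be stated in the conclusions.

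**The covariates may not all exist.** Device and operator level depend on a data form that is not shown, and enrolment has begun. Only age and SpO2 can be counted on with some confidence. The simulation treated SpO2 as uninformative, so it shows no cost from including it, but no gain either.

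**Conclusion.** The omission is certain: groups are defined by calendar period and no adjustment for recorded risk factors is specified. Whether it matters in this study cannot be determined from the documents. Under the assumed age gradient, a half-year to one-year shift towards older patients moves one-sided error from 5% to roughly 10% or 15-17%. A shift towards younger patients costs about 9 to 17 points of power (79% to 70% or 62%). Adjustment restores both. With a mild device difference the error rises only to 6-8%. The change should be made because it is cheap and uses data the plan already intends to collect. The documents support neither a claim that the comparison is already biased nor a claim that adjustment would make the two periods comparable in every respect.

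**What to change.** **Primary outcome (Section 14).** Prespecify as the primary between-group estimate a Cox model for group, adjusted for age (continuous) and SpO2 at the end of preoxygenation, and stratified by tube versus laryngeal mask if the form records device. The SpO2 value should be available: "Vitals will be recorded at the moment prior to removal of the face mask at the end of the preoxygenation period". It precedes cannula placement, which follows induction, so the cannula cannot have affected it. Use the same small model at the interim and final analyses. Keep the unadjusted logrank and Kaplan-Meier curves as supporting.

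**Secondary outcomes (Section 14).** Use regression with the same few covariates. Where events are few, such as falls to 90%, adjust for age alone or use a penalised model.

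**Interim (Section 9).** State which test, adjusted or logrank, drives the rule.

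**Power (Section 6).** State that the quoted power refers to the unadjusted logrank.

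**Conclusions.** State that adjustment removes only measured case-mix differences and that other calendar-period effects cannot be separated from the cannula.

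**Cost.** Some wording and a little more analysis. About 45 expected events limit the model to a few terms. Fields not recorded for early patients may be unrecoverable, and residual period confounding remains.
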